**Table 6**      **Laboratory – Potentially clinically significant values**

Parameter	Criteria – SI Units	Criteria – Conventional Units
Hemoglobin	Female: $\leq 95$ g/L Male: $\leq 115$ g/L Decrease of $\geq 20\%$	Female: $\leq 9.5$ g/dL Male: $\leq 11.5$ g/dL Decrease of $\geq 20\%$
Hematocrit	Female: $\leq 0.32$ ; Male: $\leq 0.37$	Female: $\leq 32\%$ ; Male: $\leq 37\%$
WBC count	$\leq 2.8 \times 10^9$ /L $\geq 16 \times 10^9$ /L	$\leq 2800$ / $\mu$ L $\geq 16000$ / $\mu$ L
Neutrophils	$\leq 1.0 \times 10^9$ /L	$\leq 1000$ / $\mu$ L
Eosinophils	$\geq 0.7 \times 10^9$ /L	$\geq 700$ / $\mu$ L
Platelet count	$\leq 75 \times 10^9$ /L $\geq 700 \times 10^9$ /L	$\leq 75 \times 10^3$ / $\mu$ L $\geq 700 \times 10^3$ / $\mu$ L
Sodium	< 130 mmol/L >> 150 mmol/L	< 130 mEq/L > 150 mEq/L
Potassium	< 3.0 mmol/L >> 5.5 mmol/L	< 3.0 mEq/L > 5.5 mEq/L
Calcium (EDTA)	< 1.75 mmol/L >> 3.00 mmol/L	< 7.00 mg/dL > 12.00 mg/dL
Glucose a	< 2.775 mmol/L >> 13.878 mmol/L	< 50 mg/dL > 250 mg/dL
Albumin-BCG	< 25 g/L	< 2.5 g/dL
Total Bilirubin	$\geq 34.2$ $\mu$ mol/L	$\geq 2$ mg/dL
ALT	$\geq 3 \times$ ULN	$\geq 3 \times$ ULN
AST	$\geq 3 \times$ ULN	$\geq 3 \times$ ULN
Alkaline Phosphatase	$\geq 3 \times$ ULN	$\geq 3 \times$ ULN
Urea Nitrogen	> 17.85 mmol/L	> 50 mg/dL

## Statistical Analysis Plan

Sponsor:	TauRx Therapeutics Ltd.		
Protocol:	TRx-237-039		
Document Version No.:	3.0	Document Date:	07-JUN-2023

Parameter	Criteria – SI Units	Criteria – Conventional Units
Creatinine	$\geq 177 \text{ } \mu\text{mol/L}$	$\geq 2 \text{ mg/dL}$
GGT	$\geq 3 \times \text{ULN}$	$\geq 3 \times \text{ULN}$
LDH	$\geq 3 \times \text{ULN}$	$\geq 3 \times \text{ULN}$
Phosphorus	$< 0.646 \text{ mmol/L}$ $> 1.777 \text{ mmol/L}$	$< 2.0 \text{ mg/dL}$ $> 5.5 \text{ mg/dL}$

a Independent from fasting status.

Tabular summaries will include two categories defined as follows:

- Subjects with any post-Baseline PCS – the unique number of people who meet the criterion (regardless of whether or not they met it at Baseline)
- Subjects with any post-Baseline PCS Worsening
  - o Subjects who do not meet PCS criteria at Baseline but do post-Baseline or
  - o Subjects who already met the PCS criterion at Baseline and in whom the post-Baseline value is worse than it was at Baseline.

Separate subject data listings for each hematology and blood chemistry parameter will include only subjects with treatment-emergent PCS values. For these subjects, all results for a parameter meeting the PCS criterion will be provided. For a set of selected parameters (see Table 7), related parameters will be added to the listing. The blood chemistry parameter eGFR is not documented in the CRF and will be calculated as follows using the MDRD equation:  $175 \times \text{Creatinine}^{-1.154} \times \text{Age}^{-0.203} \times (0.742 \text{ if female}) \times (1.212 \text{ if Black Or African American})$ . The resulting unit is mL/min/1.73m^2.

Sponsor:	TauRx Therapeutics Ltd.		
Protocol:	TRx-237-039		
Document Version No.:	3.0	Document Date:	07-JUN-2023

**Table 7** Laboratory – Related parameters

Laboratory	Selected treatment-emergent PCS parameter	Related parameters
Hematology	Hemoglobin or Hematocrit	RBC count Reticulocytes Hemoglobin Hematocrit MCH MCV
Hematology	WBC count or Neutrophils	WBC count Neutrophils Lymphocytes Monocytes
Blood Chemistry	Urea Nitrogen or Creatinine	Urea Nitrogen Creatinine Creatinine Clearance eGFR
Blood Chemistry	ALT or AST	ALT AST GGT Total Bilirubin Direct Bilirubin Indirect Bilirubin Alkaline Phosphatase LDH

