There are no clinically meaningful differences in apparent clearance (CL/F) between men and women (adjusted for differences in body weight) or between Caucasians and non-Caucasians.

In cross study comparisons, the CL/F of parent MT/LMT is lower in older subjects, possibly attributable to renal and/or hepatic impairment of varying degrees. The mean  $T_{1/2}$  of parent MT/LMT after a single oral dose in healthy older subjects is 20.7 hours as compared to approximately 15.8 hours in younger healthy volunteers.

---

 Average based on Studies TRx-237-019, TRx-237-021, and TRx-237-024.

Renal clearance of parent MT/LMT in healthy volunteers represents 13% of CL/F. Most of a radiolabeled dose (72%) is recovered in the urine, with 24% as unchanged drug and the remainder as metabolites, primarily LMT-glucuronide (28% of the dose). Apparent clearance of parent MT/LMT and total MT is decreased in subjects with renal impairment; correspondingly, AUC increases and  $T_{1/2}$  is prolonged. AUC for parent MT/LMT increases by 1.5-fold in subjects with mild impairment to 4.8-fold in subjects with severe impairment; in subjects with severe impairment,  $C_{max}$  is also affected (1.7-fold increase).  $T_{1/2}$  of parent MT/LMT after a single dose increases with worsening degree of impairment (mean 24.4 hours, 29.3 hours, and 46.2 hours in mildly, moderately, and severely impaired subjects, respectively), relative to a mean  $T_{1/2}$  of 15.7 hours in generally younger healthy controls [and in a cross-study comparison, 21.3 hours in older healthy volunteers)]; the longest  $T_{1/2}$  was 81.9 hours in a subject with severe impairment.

Apparent clearance of parent MT/LMT (but not total MT) is decreased in subjects with mild to moderate hepatic impairment; some of the subjects with mild to moderate hepatic impairment also had markedly elevated bilirubin (including due to Gilbert's syndrome) and/or history of cholecystectomy. When compared to control subjects with normal hepatic function,  $C_{max}$  was 2.1- to 3.2-fold higher with mild and moderate impairment, respectively; AUC was 1.4- to 2.1-fold higher, respectively. Mean  $T_{1/2}$  was prolonged 54% to 87% relative to a mean  $T_{1/2}$  of 15.2 hours in generally younger healthy controls (and in a cross-study comparison, 21.3 hours in older healthy volunteers as noted above); the longest  $T_{1/2}$  was 50.1 hours in a subject with mild impairment.

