## **11 SUBJECT ENROLLMENT AND WITHDRAWAL**

### **11.1 Inclusion Criteria**

To be eligible for enrollment in this study, a subject must meet all of the following inclusion criteria:

1. AD, encompassing probable AD and MCI-AD based on 2011 NIA/AA criteria:
  - All cause dementia and probable AD (probable AD)  
In brief, subjects with probable AD dementia must have insidious onset,

worsening impairment in at least two cognitive areas (learning and recall, language, executive function, visuospatial skills), sufficient to significantly interfere with work or usual activities, that is not explained by delirium, drugs, major psychiatric disorder, medical illness, cerebrovascular disease, other forms of dementia, or neurological disorder. The accuracy of the diagnosis will be confirmed independently by the diagnosing physician at site.

OR

- MCI-AD

In subjects with MCI-AD, there should be evidence of concern about a change in cognition, in comparison with the person's previous level verified by a knowledgeable informant or clinician. Other mild cognitive deficits may also be present, but there must be preservation of independence in functional abilities. Subjects should not meet the criteria for dementia. The cognitive changes must be mild and there must be no evidence of a significant impairment in social or occupational functioning. Impairments must not be explained by delirium, drugs, major psychiatric disorder, medical illness, cerebrovascular disease, other forms of dementia, or neurological disorder.

2. Documented PET scan that is positive for amyloid; if most recent PET scan was performed >3 years prior to Screening and was negative, it may be repeated (a negative amyloid PET scan within the 3 years prior to Screening is exclusionary)
3. MMSE score of 16-27 (inclusive) at Screening, subject to stratification requirements
4. Global CDR score of 0.5 to 2 at Screening (if 0.5, including a score of >0 in one of the functional domains: Community Affairs, Home and Hobbies, or Personal Care)
5. Age <90 years at Screening
6. Females must meet one of the following:
  - Surgically sterile (hysterectomy, bilateral salpingectomy / oophorectomy) for at least 6 months minimum
  - Have undergone bilateral tubal occlusion / ligation at least 6 months prior
  - Post-menopausal for at least 1 year

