8. Any physical disability that would prevent completion of study procedures or assessments (e.g., blindness or significant uncorrected visual impairment, deafness or significant hearing loss not corrected by hearing aids, non-AD-related speech impairment)
9. History of swallowing difficulties (note: study drug should be swallowed whole and MUST NOT be broken, crushed, chewed, or dissolved in fluids prior to ingestion)
10. Pregnant or breastfeeding
11. G6PD deficiency based on World Health Organization (WHO) classification (<60% of normal, i.e., <6.1 U/g hemoglobin [Hgb])
12. History of significant hematological abnormality or current acute or chronic clinically significant abnormality, including:
  - History of hemoglobinopathy, myelodysplastic syndrome, hemolytic anemia, or splenectomy
  - Screening Hgb value (confirmed upon repeat) below age/sex appropriate lower limit of the central laboratory normal rangeSubjects in whom folate is <4.0 ng/mL may be entered into the study provided folate supplementation (approximately 1 mg/day) is initiated and maintained for the duration of the study; subjects in whom vitamin B12 is <150 pg/mL can be allowed if the investigator confirms that it does not affect the cognitive state of the subject and that the subject is supplemented as appropriate prior to the initiation of study drug
13. Abnormal serum chemistry laboratory value at Screening deemed to be clinically significant by the investigator. In addition, subjects with either of the following abnormalities must be excluded:
  - Creatinine clearance <30 mL/min, estimated by the central laboratory according to the Cockcroft and Gault equation
  - TSH above laboratory normal range (subject may be treated [if clinically indicated based on further laboratory testing] and re-screened after 90 days)
14. Clinically significant cardiovascular disease or abnormal assessments (based on the investigator's interpretation of the locally obtained ECG) such as:
  - Hospitalization for acute coronary syndrome (acute myocardial infarction or unstable angina) or symptoms consistent with angina pectoris, within the 12 months preceding Baseline
  - Signs or symptoms of clinical heart failure within the 12 months preceding Baseline
  - Atrial fibrillation on screening ECG or history of atrial fibrillation that is not currently controlled (heart rate  $\geq$ 85 bpm and/or inappropriate anticoagulation)

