### ***16.11.3 Other Safety Reasons Requiring Discontinuation of Study Drug***

If the calculated creatinine clearance is <30 mL/min and renal concerns arise, study drug should be discontinued.

For any other safety concerns that may arise during treatment, the Medical Monitor or 24-hour medical contact number (see Section 4) should be contacted to discuss possible discontinuation of study drug.

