The treatmentwise correlation (HMTM 16 mg/day, HMTM 8 mg/day, and control) between the G6PD value at Screening and the change in hemoglobin from Baseline up to Week 52 visit will be analyzed. Separate scatter plots will present the values of G6PD and hemoglobin, along with the treatmentwise p-values based on the parametric Pearson correlation. If the Week 52 visit value is not available, the last available on-treatment value will be used. In addition, the change in hemoglobin from Baseline up to Week 52 visit will be analyzed using an ANCOVA, including the randomization stratification variables (see Section 2.6) as fixed factors, the hemoglobin Baseline value and the total duration of exposure (see Section 5.12.1) as covariates, and the treatment indicator; with the Kenward and Roger method used for calculating the denominator degrees of freedom for the tests of fixed effects. This will be performed in two G6PD subgroups: one subgroup includes all subjects with a G6PD Screening value between 60 and 80 percent relative to the lower bound of the laboratory’s reference range, and one subgroup includes all subjects with a G6PD Screening value higher than 80 percent relative to the lower bound of the laboratory’s reference range.

All laboratory data (hematology, and blood chemistry) will be provided in subject data listings, including flags for values outside the reference range, as well as for values being potentially clinically significant (PCS, see Table 6), and for value obtained at a local laboratory. When there are thresholds provided for low and high values, they will be handled separately. A listing will also be provided that details the normal ranges from the central laboratory for all parameters in this study.

Sponsor:	TauRx Therapeutics Ltd.		
Protocol:	TRx-237-039		
Document Version No.:	3.0	Document Date:	07-JUN-2023

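### SAP Table 6 has no creatinine-clearance criterion, so post-Baseline falls below the protocol's 30 mL/min figure are not counted by treatment arm

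*SAP*

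**What the plan says.** **Protocol.** Exclusion criterion 13 (Section 11.2) removes subjects at Screening with "Creatinine clearance <30 mL/min, estimated by the central laboratory according to the Cockcroft and Gault equation". On study, Section 16.11.3 uses the same figure with a condition attached: "If the calculated creatinine clearance is <30 mL/min and renal concerns arise, study drug should be discontinued". Section 8.1.3.1 reports that "AUC for parent MT/LMT increases by 1.5-fold in subjects with mild impairment to 4.8-fold in subjects with severe impairment". Section 8.2 names creatinine clearance as the most important predictor of whether a subject exceeds the exposure threshold. The age limit is "Age <90 years at Screening".

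**SAP Section 5.12.3.** Table 6 defines PCS values. Its renal rows are creatinine (177 µmol/L or 2 mg/dL and above) and urea nitrogen (above 17.85 mmol/L or 50 mg/dL). There is no row for creatinine clearance or eGFR. Subjects meeting a criterion are tabulated in two categories: any post-Baseline PCS value, and post-Baseline worsening. The PCS listings are restricted: "Separate subject data listings for each hematology and blood chemistry parameter will include only subjects with treatment-emergent PCS values". For context, "For a set of selected parameters (see Table 7), related parameters will be added to the listing". In Table 7, clearance and eGFR appear only as related parameters, when creatinine or urea nitrogen is already PCS. On eGFR the SAP says: "The blood chemistry parameter eGFR is not documented in the CRF and will be calculated as follows using the MDRD equation". No cut-off is attached to it.

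**Other laboratory outputs.** The SAP also says: "All laboratory data (hematology, and blood chemistry) will be provided in subject data listings, including flags for values outside the reference range". Every parameter is summarised by visit, including its minimum, and shift tables are given against the reference range. Appendix 12.3.1 treats creatinine clearance as a blood chemistry parameter whose lowest value is the worst. Section 6.13.3 repeats the PCS approach for the open-label phase.

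**The concern.** The PCS tables are where a reader of the study report will look for the number of subjects with a notable renal change in each arm. They judge everyone by a fixed serum creatinine, while the protocol judges renal function by clearance, which also depends on age, sex and weight. In older women and lighter older men, clearance can pass 30 mL/min well before creatinine reaches 2 mg/dL.

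The figure matters in this trial because exposure depends on renal function and the hematological margin is narrow. Protocol Section 8.1.2 places hematological effects at 2.1-fold (rat) and 1.2-fold (minipig) the human exposure at 16 mg/day, and hemolytic anemia is an event of special interest. Without a clearance criterion, the report cannot say from its tables how many subjects fell below 30 mL/min on treatment, in which arm, or what their hemoglobin did.

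The hemoglobin row of Table 6 shows that the SAP can follow the protocol. It includes a fall of 20% or more, in line with the 20% fall that Protocol Section 16.11.1 lists as a sign of possible hemolytic anemia. The renal rows have no such link.

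**Working it through.** **1. The plan's own figures.** The paired units in Table 6 agree, using standard conversion factors that are not in the documents: 2 × 88.4 = 176.8, given as 177 µmol/L; 50 × 0.357 = 17.85 mmol/L.

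**2. Formula.** The protocol names Cockcroft-Gault but does not print it. The usual form is assumed: clearance = (140 − age) × weight × s ÷ (72 × creatinine), with s = 0.85 for women and 1 for men.

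- Creatinine at which clearance is 30 mL/min: (140 − age) × weight × s ÷ (72 × 30), that is, ÷ 2160.
- Clearance at the Table 6 cut-off of 2.0 mg/dL: (140 − age) × weight × s ÷ (72 × 2.0), that is, ÷ 144.

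**3. Examples.** Ages and weights are assumptions; the ages lie within the eligible range.

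| Assumed subject | (140 − age) × weight × s | Creatinine at 30 mL/min (mg/dL) | Clearance at 2.0 mg/dL (mL/min) |
|---|---|---|---|
| Woman, 75, 65 kg | 65 × 65 × 0.85 = 3591.25 | 1.66 | 24.9 |
| Woman, 80, 60 kg | 60 × 60 × 0.85 = 3060 | 1.42 | 21.25 |
| Woman, 85, 55 kg | 55 × 55 × 0.85 = 2571.25 | 1.19 | 17.9 |
| Man, 85, 70 kg | 55 × 70 = 3850 | 1.78 | 26.7 |
| Man, 75, 80 kg | 65 × 80 = 5200 | 2.41 | 36.1 |

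In the first four rows there is a range of creatinine values in which clearance is below 30 mL/min and the creatinine criterion is not met. In the last row the creatinine criterion is met first, while clearance is still above 30.

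**4. A change on study.** The woman of 80 weighing 60 kg, with creatinine rising from 1.0 to 1.9 mg/dL, goes from 3060 ÷ 72 = 42.5 to 3060 ÷ (72 × 1.9) = 22.4 mL/min with no creatinine PCS flag. She enters the renal PCS outputs only if urea nitrogen also exceeds 50 mg/dL.

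**5. Where the gap opens.** It exists below the weight 30 × 72 × 2 ÷ ((140 − age) × s) = 4320 ÷ ((140 − age) × s).

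| Age | Women below (kg) | Men below (kg) |
|---|---|---|
| 70 | 72.6 | 61.7 |
| 75 | 78.2 | 66.5 |
| 80 | 84.7 | 72.0 |
| 85 | 92.4 | 78.5 |

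**6. Whether another output supplies the count.**

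- The full listings show each value with reference-range and PCS flags, but give no tally and no marker at 30 mL/min.
- The by-visit minimum can show that at least one subject in an arm fell below 30, but not how many did.
- The shift tables use the reference range, not 30 mL/min.
- The Renal Function Impairment event group (SAP 5.12.2) relies on reported events. Under Protocol Section 16.1 a laboratory abnormality becomes an adverse event when the investigator deems it clinically significant.
- The event groupings are split by clearance at or below 50 versus above 50 mL/min, but at Baseline only.
- The hemoglobin PCS listing carries other red-cell parameters, not clearance; the renal listing carries no hemoglobin.

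None of these gives a count by arm of subjects below 30 mL/min after Baseline.

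**The case against.** The strongest reply is that little is hidden. Every clearance value is listed and summarised, with minima and shift tables. Anemia and renal event groups are tabulated by Baseline clearance. Hemoglobin has its own PCS criteria whatever the renal function, so a subject losing both clearance and hemoglobin is caught through hemoglobin. PCS cut-offs are descriptive screens. SAP Section 10 states that version 3.0 followed the snapshot and partial unblinding, so a new criterion in Section 5.12.3 would be post hoc. All of this stands, and it limits the point to a missing count and listing.

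It also rules out several stronger readings that a reader might infer:

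- *That these subjects are never listed, or that the SAP flags renal change only at the two cut-offs.* The full listings with reference-range flags contradict both.
- *That many subjects are affected.* The documents give no distribution of weight, creatinine or clearance, and subjects below 30 mL/min at Screening are excluded.
- *That a fall below 30 would show in the shift tables as low to low.* That needs the laboratory's reference range for clearance, which the documents do not give.
- *That the 4.8-fold AUC applies to exactly these subjects.* The protocol does not tie its severe-impairment group to 30 mL/min, and exposure analyses belong to a separate plan.
- *That remaining on drug below 30 mL/min breaks the protocol, or that the entry and on-study rules contradict each other.* The on-study rule is conditional on renal concerns. The two rules serve different purposes and need not match.

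**Conclusion.** The point holds as a limited reporting gap. Table 6 has no clearance criterion, so a subject below 30 mL/min with creatinine under 2 mg/dL and urea nitrogen at or below 50 mg/dL is not counted as a renal PCS case and does not appear in the renal PCS listings. No other planned output counts such subjects by arm.

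At the Table 6 creatinine cut-off, clearance in the four assumed examples where the gap exists is already about 18 to 27 mL/min. This rests on the usual Cockcroft-Gault form and on assumed ages and weights. It shows that the gap can occur in older women and lighter older men, not how often it does. Efficacy analyses are untouched.

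**What to change.** - In SAP Table 6, add post-Baseline creatinine clearance below 30 mL/min as a descriptive PCS criterion, tabulated in the existing any and worsening categories.
- In SAP Table 7, add creatinine clearance as a selected parameter, with hemoglobin and reticulocytes among its related parameters.
- Apply both to Sections 5.12.3 and 6.13.3.
- Label the criterion as added after the double-blind snapshot. The cut-off is already in the protocol, so its value was not chosen from the data, although the decision to tabulate it comes late.

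The cost is one row in each of two tables, the matching shells, and a small number of table and listing re-runs. Clearance is already a laboratory parameter in the SAP (Table 7, Appendix 12.3.1). This concerns reporting only; no clinical rule is proposed.

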#### 5.12.4. Vital Signs

The Baseline value, the actual value and change from Baseline to each on study evaluation and to the last available on-treatment value will be summarized, with the Baseline value being defined as the last non-missing value prior to first dose of study drug.

A similar summary will be generated for blood pressure values obtained on Day 1 (pre-dose and post-dose) in the subset of subjects identified as concomitantly taking the following pharmacological subgroup of serotonergic drugs at Baseline: SSRIs, SNRIs, or MAOIs (see latest version of the Serotonergic Drugs List, Section 5.8, and Section 12.4).

Sponsor:	TauRx Therapeutics Ltd.		
Protocol:	TRx-237-039		
Document Version No.:	3.0	Document Date:	07-JUN-2023

PCS vital sign changes are defined in Table 8 and will need to be calculated and identified prior to further analysis. The number and percentage of subjects meeting these criteria (any post-Baseline PCS) will be summarized according to the definition described in Section 5.12.3. Increasing and decreasing changes will be categorized separately.

Vital sign measurements will be presented in a subject data listing.

**Table 8      Vital signs – Potentially clinically significant values**

Parameter	Criteria
Systolic Blood Pressure	Increase of $\geq 20$ mmHg from Baseline and $\geq 180$ mmHg
	Decrease of $\geq 20$ mmHg from Baseline and $\leq 90$ mmHg
Diastolic Blood Pressure	Increase of $\geq 15$ mmHg from Baseline and $\geq 105$ mmHg
	Decrease of $\geq 15$ mmHg from Baseline and $\leq 50$ mmHg
Pulse	Increase of $\geq 15$ beats/min from Baseline and $\geq 120$ beats/min
	Decrease of $\geq 15$ beats/min from Baseline and $\leq 50$ beats/min
Weight	Decrease of $\geq 7\%$ from Baseline
	Decrease of $\geq 10\%$ from Baseline
	Increase of $\geq 7\%$ from Baseline
	Increase of $\geq 10\%$ from Baseline

